At the screening visit, an ECG will be conducted in order to examine the heart and ensure participant safety; an adult cardiologist will also evaluate all individuals during the screening phase. If during the MRI/MRS scans we unexpectedly discover something that warrants further inspection, we will refer the participant to her primary care provider for follow-up, along with the MRI/MRS report that shows the findings. Any costs related to following up on unexpected findings will be the responsibility of her and/or her insurance provider. In conjunction with the brain scans performed pre- and post-treatment, a brief battery of cognitive tests will be administered, to evaluate change associated with creatine or placebo. Trained psychometricians administer tests on the day of scanning. Scoring is done blind to subjects' group status, clinical ratings and imaging results. The cognitive testing battery instruments were

chosen because they are sensitive to frontal lobe integrity: the Wisconsin Card Sorting Task (WCST)[129], the Stroop Color-Word Test[130, 131], and the Wechsler Memory Scale (WMS-IV)[132]. Furthermore, the WCST[133], Stroop Test[134] and WMS-IV [90] each have been associated with performance deficits in MA users.

TABLE 2A Schedule of Procedures for Methamphetamine-dependent Females												
	Screening	Treatment Phase								Follow Up Phase		
Study Week →	-2 to 0^a	1*	2*	3*	4*	5*	6*	7*	8*	9	10	11
Informed Consent, Demographics	X											
Medical History & Physical Exam, ECG	X											
Hematology & Chemistries	X									X		
Phlebotomy for Creatinine Levels	X				X					X		
HIV	X											
Pregnancy Test and vital signs	X	X	X	X	X	X	X	X	X	X	X	X
PRISM Diagnostic Interview	X											
ASI	X									X		
Randomization to Creatine or Placebo	X											
Treatment with Creatine or Placebo		X	X	X	X	X	X	X	X			
Urine Drug Screen / Other Drug Use	X	X	X	X	X	X	X	X	X	X	X	X
Concomitant Medications	X	X	X	X	X	X	X	X	X	X	X	X
Food Frequency Questionnaire	X									X		
Cognitive Tests: WCST, STROOP and WMS-IV (with WASI vocabulary)***	X									X		
Adverse Events		X	X	X	X	X	X	X	X	X	X	X
Treatment Program Attendance	X	X	X	X	X	X	X	X	X	X	X	X
Clinical Scales: HAMD**, BAI**, CGI-S**, C-SSRS	X	X	X	X	X	X	X	X	X	X	X	X

³¹ P-MRS and ¹ H-MRS****	X									X		
*During the 8 Treatment Weeks, MA Subjects Have 2 Study Visits Per Week (separated by \geq 48 hours)												
**Procedure will be collected at one of the twice weekly visits												

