***MA subjects with difficulty scheduling the cognitive testing appointment may be allowed to omit these measures and continue in the study as to not delay treatment and in order to facilitate timely enrollment, which is critical for this population.												
****If an individual is screened and determined to be a good fit for study participation but also has a contraindication to MRI scanning, the principal investigator may allow them into the study, however, they will not be scanned for their safety.												
CGI-S = Clinical Global Impressions-Severity Depression Score; C-SSRS = Columbia-Suicide Severity Rating Scale; HAMD = Hamilton Rating Scale for Depression; BAI = Beck Anxiety Inventory; PRISM = Psychiatric Research Interview for Substance and Mental Disorders; STROOP = Stroop Color Word Test; WCST = Wisconsin Card Sorting Test; WMS-IV = Wechsler Memory Scale; WASI = Wechsler Abbreviated Scale of Intelligence; ASI = Addiction Severity Index.												
^a Screening may happen over the course of 2-3 visits.												

TABLE 2B Schedule of Procedures for Healthy Controls

	Screening									Final Visit
Study Week →	-1 to 0 ^a	1	2	3	4	5	6	7	8	9
Informed Consent, Demographics	X									
Medical History & Physical Exam, ECG	X									
Hematology & Chemistries	X									
Phlebotomy for Creatinine Levels	X									
HIV	X									
Pregnancy Test	X									X
PRISM Diagnostic Interview	X									
Food Frequency Questionnaire	X									X
Urine Drug Screen / Other Drug Use	X									X
Concomitant Medications	X									X
Vital Signs	X									X
Cognitive Tests: WCST, STROOP and WMS-IV (with WASI vocabulary)	X									X
Treatment Program Attendance	X									X
Clinical Scales: HAMD**, BAI**, CGI-S**, C-SSRS	X									X

³¹ P-MRS and ¹ H-MRS	X									X
CGI-S = Clinical Global Impressions-Severity Depression Score; C-SSRS = Columbia-Suicide Severity Rating Scale; HAMD = Hamilton Rating Scale for Depression; BAI = Beck Anxiety Inventory; PRISM = Psychiatric Research Interview for Substance and Mental Disorders; STROOP = Stroop ColorWord Test; WCST = Wisconsin Card Sorting Test; WMS-IV = Wechsler Memory Scale; WASI = Wechsler Abbreviated Scale of Intelligence.										
^a Screening may happen over the course of 2-3 visits.										

RISKS AND BENEFITS TO STUDY PARTICIPANTS

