Overall Analytic Strategy: The analyses proposed are generalized estimating equations (GEE) regression modeling, which will be used for our longitudinal data analyses with group comparison across treatment visits for the variables of metabolite levels, depression/anxiety symptoms, and cognitive tests. GEE allows robust estimations of standard errors and permits adjustment for time-varying covariates. We assume that measurements made closer in time are more correlated than those made farther apart. Thus, first-order autoregressive structure is assumed. For our repeated measurement data, GEE fits a population-averaged model with working correlation structure to statistically evaluate the time effect of creatine supplementation. We will control for age, other drug abuse, anxiety scores, and tissue partial volume effects in each GEE model. Sidak multiple comparison procedure will be employed to adjust for family wise error (FWE) rate. The Sidak tests make conservative controls of FWE, giving slightly smaller adjusted p-values than the Bonferroni correction.

Overall Power and Sample Size Calculations: For this pilot study, considering a 20% attrition rate, 95 participants will be recruited to achieve a sample size of 75. To determine the minimum effect that would likely be detected with a sample size of 75, a power analysis was performed. Effect for the power analysis was specified as average baseline (over two measures) HAM-D scores compared with average HAM-D scores during active treatment (over eight measures). A gradual onset of effect during active treatment is assumed, starting with an effect of 0 and ending with an effect of 0.5, resulting in an average effect during treatment of 0.25. The effect to be tested was treated as a linear combination of the separate measures (y^*), and a pattern of correlation of 0.5 was used. This generated a standard deviation [105] for y^* that will be different from the within-occasion SD for Y itself. Then the effect magnitude specified was divided by the $SD(y^*)$ to generate an "effective" or de facto effect size, which resulted in an effect size of 1.09 with a power of 0.87.

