Statistical Analysis for Specific Aim 3: Cognitive testing data with a repeated measures design will evaluate the cognitive improvement after 8 weeks of creatine supplementation, specifically in executive and working memory deficits, found in MA users. The relative improvements on WCST, Stroop and WMS-IV scores associated with creatine versus placebo will be tested conservatively with the assumption of independence among comparisons. Independent variables include a time variable of "visit" (baseline and 8 weeks of treatment), creatine" (placebo or creatine group), and an interaction term, "creatine \times visit", where a significant interaction will indicate significant differences between treatments. The depression effect will be

tested by stratifying depressed and non-depressed MA users. Power and Sample Size Calculations: Previous reports, meta-analysis, and our preliminary data suggest that the cognitive deficits of MA users have medium-to-large (0.5 to 0.8) effect size, especially in the episodic memory, compared to healthy subjects. Thus, the proposed sample size (n=76) will have enough power (> 80%) based on Cohen's guidelines with adjusted Sidak p-values of 0.0169. [137, 138]

ADMINISTRATIVE RESPONSIBILITIES

Resources:

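### Aim 3: the creatine × visit test is in effect a change-score comparison; adjusting for the baseline score would be more precise and needs no new data

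*Combined protocol and SAP*

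**What the plan says.** Statistical Analysis for Specific Aim 3 defines a visit variable with two levels, "baseline and 8 weeks of treatment", a treatment-group variable and their interaction, "where a significant interaction will indicate significant differences between treatments". The group main effect is in the model, so the arms may have different baseline means.

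Overall Analytic Strategy sets the model family: "The analyses proposed are generalized estimating equations (GEE) regression modeling". On the working correlation it says: "Thus, first-order autoregressive structure is assumed". On covariates it says: "We will control for age, other drug abuse, anxiety scores, and tissue partial volume effects in each GEE model". The baseline value of the cognitive score is not listed. The same paragraph notes that "GEE allows robust estimations of standard errors and permits adjustment for time-varying covariates", and it does not say whether the anxiety score is the baseline value or the value at each visit.

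Study Procedures places the testing alongside the scans before and after treatment: "a brief battery of cognitive tests will be administered, to evaluate change associated with creatine or placebo". A footnote to Table 2A adds that "MA subjects with difficulty scheduling the cognitive testing appointment may be allowed to omit these measures and continue in the study".

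**The concern.** Subtracting the baseline score forces its coefficient to be 1. The coefficient that minimises the variance is the regression slope of week 8 on baseline, which equals r when the SDs are equal. When that slope is well below 1, subtraction adds the noise of the baseline measurement to the comparison.

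The stake is precision, not validity. With equal SDs and r below 0.5, the planned test is even less precise than comparing week-8 scores and ignoring baseline. Baseline testing then costs precision, although the same scores used as an adjuster would add it. Aim 3 has little to spare: it is planned on 76 women and a Sidak-reduced alpha of 0.0169 for each of three tests.

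**Working it through.** **The plan's own figure.** Sidak for three tests: 1 − 0.95^(1/3) = 0.01695, which the plan gives as 0.0169. With 38 per arm and two-sided alpha 0.0169, a two-sample t-test on a single-visit score has power 0.85 at an effect of 0.8 SD and 0.40 at 0.5 SD. The stated power above 80% is therefore reached only near the top of the plan's 0.5 to 0.8 range. That range is also a deficit against healthy subjects, not a creatine–placebo difference. This is a separate matter, and the present point does not depend on it.

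**Inputs.** From the plan: two visits, three tests, alpha 0.0169 (taken as two-sided), n=76 (38 per arm). Assumed, because the documents give no values: the baseline-to-week-8 correlation r, the week-8/baseline SD ratio k, and an effect of 0.5 baseline SD for the power illustration.

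**Step 1: what the interaction estimates.** With two visits, first-order autoregression is a single correlation. GEE fits to simulated complete data (n=76, age as a visit-fixed covariate) gave an interaction equal to the difference in mean change to at least 10 digits at k = 0.8, 1.0 and 1.25. The identity therefore does not need equal SDs.

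**Step 2: variances.** With baseline SD 1 and week-8 SD k:

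- change score: 1 + k² − 2rk
- baseline-adjusted: k²(1 − r²)
- proportional saving: (1 − rk)² / (1 + k² − 2rk)

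The saving is never negative and is zero when rk = 1. At k=1 it reduces to (1 − r)/2. Example, k=1 and r=0.3: change 1.40, adjusted 0.91, saving 1 − 0.91/1.40 = 35%. Estimating the slope multiplies the adjusted variance by 1 + 1/(N−4) = 1 + 1/72 = 1.0139 at N=76.

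| Saving (large sample / N=76) | r=0.3 | r=0.5 | r=0.7 | r=0.8 |
|---|---|---|---|---|
| k=1 | 35% / 34% | 25% / 24% | 15% / 14% | 10% / 9% |
| k=1.25 | 22% / 21% | 11% / 10% | 2% / 1% | 0% / −1% |
| k=0.8 | 50% / 49% | 43% / 42% | 37% / 36% | 36% / 35% |

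**Step 3: power illustration.** Noncentral t, 38 per arm all tested at both visits, df 74 for change and 73 for adjusted, slope estimated:

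| Power (change → adjusted) | r=0.3 | r=0.5 | r=0.7 | r=0.8 |
|---|---|---|---|---|
| k=1 | 0.28 → 0.44 | 0.40 → 0.53 | 0.64 → 0.72 | 0.84 → 0.87 |
| k=1.25 | 0.21 → 0.27 | 0.30 → 0.33 | 0.49 → 0.50 | 0.68 → 0.67 |
| k=0.8 | 0.34 → 0.65 | 0.48 → 0.75 | 0.72 → 0.91 | 0.88 → 0.98 |

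Week-8 scores alone at k=1 give 0.40 whatever r is. At r=0.3 the planned test (0.28) falls below that.

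**Step 4: simulation.** ANCOVA, 20,000 trials per setting: savings at k=1 of 33.8%, 23.5%, 13.3% and 8.7%; a 1.1% loss at k=1.25, r=0.8; type I error 0.016 to 0.018; both estimators unbiased. The common-baseline model with estimated covariance, 4,000 trials per setting, gave 34.7%, 23.2%, 12.6% and 8.5% at k=1 and a 1.7% loss at k=1.25, r=0.8. Its uncorrected model-based test had average type I error 0.0199 against 0.0169.

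**Step 5: incomplete pairs.** With 20% missing week 8 and the planned GEE keeping women who have only a baseline score, ANCOVA still saved about 29%, 19% and 7% at r = 0.3, 0.5 and 0.8 (k=1).

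**The case against.** The planned test is valid, the trial describes itself as a pilot, and this is its third aim. All of that stands, and it is why the point is a recommendation and not an error.

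The sizes are conditional. The documents give no r or SDs for the cognitive tests. The only correlation they use is 0.5, for the HAM-D in the main power calculation; at that value and equal SDs, change scores and week-8 scores alone tie, and adjustment still saves 25%. The power values assume 38 per arm, while the Design section randomises 123 (about 98 after 20% attrition, before omitted tests), and they borrow an effect size. They are illustrations only.

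The exact identity may also fail in practice. Table 2A collects the anxiety scale weekly, so a visit-specific covariate is a natural reading, and tests may be omitted. In either case the complete-data figures do not apply directly. Step 5 shows that the gain shrinks under missing follow-up but remains. No figure is available for visit-specific anxiety adjustment.

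A smaller change would be to keep the GEE and drop the group main effect. That works at equal SDs but less well otherwise, because the working model assumes one common variance. At k=1.25, r=0.8 the implied slope is rk/[(1+k²)/2] = 1/1.281 = 0.780. The variance is then 1.5625 + 0.780² − 2(0.780)(1) = 0.611, against 0.5625 for the change score, a loss of about 9%. ANCOVA or an unstructured covariance avoids this.

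**Conclusion.** The point holds as an efficiency improvement confined to Aim 3, the only aim whose interaction term is written out. With complete pairs and visit-fixed covariates, the planned test is a change-score comparison. Baseline adjustment saves (1−r)/2 of its variance at equal SDs, which is 35% to 10% for assumed r of 0.3 to 0.8. Across the SD ratios examined, the result at N=76 runs from a 49% saving to a loss of 1% by formula (up to 1.7% in simulation of the common-baseline model). Confidence in the direction is high. Confidence in the size is limited by the unknown r and SDs and by the handling of anxiety scores and omitted tests. Nothing here questions the validity of the planned test.

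**What to change.** Before unblinding, specify for WCST, Stroop and WMS-IV a repeated-measures model with a baseline mean common to both arms: visit and arm × post-treatment visit, no arm main effect, unstructured 2×2 covariance. Test the arm difference at the post-treatment visit with a small-sample correction such as Kenward-Roger. The uncorrected test was slightly liberal in simulation, and the corrected one was not simulated here, so its type I error should be checked. Like the planned GEE, this model keeps women with only one score. ANCOVA of the week-8 score on arm and baseline score is the simpler complete-case counterpart and held its level in simulation.

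State that the other covariates, anxiety in particular, enter as baseline values. Extend the model to the metabolites only if they are to be analysed in the same way as Aim 3.

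The cost is a change of analysis wording. Because the analysis plan sits in the protocol, the change follows the approval route under Reporting Protocol Changes (IRB, FDA and the NIDA program officer). The baseline tests are already scheduled.

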In addition to these **Specific Aims**, we will monitor subjects' MA use, as improvements in brain bioenergetics, mood/anxiety and may decrease MA usage. Therefore, we will record urine drug testing results, to determine whether creatine vs. placebo is associated with a greater number of MA-free tests during the 8 weeks of randomized treatment.

PARTICIPANT SELECTION CRITERIA

123 women will be randomly assigned in a 1:1 ratio to either creatine or placebo for eight weeks. Table 1 outlines eligibility criteria.

TABLE 1 INCLUSION AND EXCLUSION CRITERIA

INCLUSION CRITERIA:

- Female gender, ages 18-55 inclusive
- Current primary diagnosis of MA dependence or abuse, with MA preferred drug of abuse (Lifetime MA use > 20 grams)
- Current diagnosis of Major Depressive Disorder (MDD)
- Current HAMD score ≥ 10
- Clinical Global Impressions–Severity (CGI-S) depression score ≥ 4
- If taking a psychotropic medication for depressed mood, regimen must be stable for ≥ 4 weeks prior to randomization

EXCLUSION CRITERIA:

- Persons unable to provide adequate informed consent
- Persons who are at clinically significant suicidal or homicidal risk
- Primary substance-related diagnosis *other than* MA dependence or abuse
- Comorbid substance dependence diagnosis, other than nicotine (substance abuse diagnoses are not excluded)
- Positive pregnancy test, due to the unknown effects of MRI scanning on the unborn fetus
- Positive test for antibody to the Human Immunodeficiency Virus (HIV)
- History of renal disease
- Clinically significant medical or neurological illness identified by history, physical exam and laboratory testing
- Known or suspected intellectual disability, or developmental disorder, e.g. autism
- History of hypersensitivity reaction to creatine

WITHDRAWAL / EARLY TERMINATION CRITERIA:

- Withdrawal of informed consent
- Suicide attempt
- Psychiatric hospitalization
- Onset of bipolar disorder or psychotic disorder
- Positive pregnancy test
- Incarceration
- Inability to comply with study protocol

▪ Treatment with electroconvulsive therapy (ECT)▪ Increase in HAMD score > 25% from baseline▪ Serious adverse event

▪ HEALTHY CONTROL SUBJECTS:
 
▪ Female gender, ages 18-55 inclusive▪ No current or past DSM-5 diagnosis, as determined by clinical and structured interviews▪ No first-degree relatives with known or suspected DSM-5 diagnosis

DESIGN

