The proposed study will use a randomized, double-blind, placebo-controlled design. 123 participants will be randomly assigned in a 1:1 ratio to placebo or 5 grams of daily creatine treatment for eight weeks. We also plan to recruit 24 age-matched females (18-55).

STUDY PROCEDURES

All procedures performed by study personnel are research-related. None of the study activities will be considered standard of care. There will be no cost to study subjects for their participation. Participants will be compensated for their time and travel. Table 2A and 2B outlines the schedule of study procedures for treated participants and healthy controls.

Consent will be obtained before any study procedures are initiated. Potential participants will be informed of the study and offered a consent form to review. They will be encouraged to discuss study participation with their relatives. If a potential participant expresses interest in study participation, the informed consent process will be conducted. After the informed consent process, individuals will be offered time to consider study participation and to ask questions. Subjects and parents/guardians will have the opportunity to discuss the study with a study team member in a setting free of coercion. The language of the informed consent form is written at a level easily understood by the subject and any questions asked by the subject will be answered honestly and free of bias. A specific meeting time will be set up between a study team member and the participant where the entire informed consent document will be carefully explained in its entirety. The length of the meeting will be designed so there is the necessary amount of time for all questions to be answered.

Randomization of participants to the two treatment conditions will take place according to a randomization list generated prior to the start of recruitment. 47 (50%) will be randomized to placebo. The study will be conducted as a double-blind trial, with neither participants nor research staff aware of participant assignment. Except in cases of medical emergency, the double-blind will not be "broken" until recruitment is closed and the final participant has completed 8 weeks of treatment with investigational drug. There is no "washout period" for any participant in this study, and participants randomized to placebo will continue treatment with a psychotropic medication throughout their time in the study.

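### Aim 3's claim of more than 80% power does not follow from its stated inputs, and its effect size is a deficit versus healthy subjects, not a creatine-placebo difference

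*Combined protocol and SAP*

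**What the plan says.** The power text under Statistical Analysis for Specific Aim 3 starts from earlier reports and preliminary data that "cognitive deficits of MA users have medium-to-large (0.5 to 0.8) effect size, especially in the episodic memory, compared to healthy subjects". From this it concludes that "the proposed sample size (n=76) will have enough power (> 80"%, citing Cohen's guidelines and a Sidak-adjusted level of 0.0169. No calculation is shown, and neither sidedness nor a pre-post correlation is given.

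The same section defines the test. Cognition is measured at baseline and after 8 weeks, and the model has visit, treatment and their product, "where a significant interaction will indicate significant differences between treatments".

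Three other places bear on the claim:

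- Overall Power and Sample Size Calculations says "95 participants will be recruited to achieve a sample size of 75", allowing for 20% attrition. For its HAM-D calculation, "a pattern of correlation of 0.5 was used". That is the only correlation in the power text.
- Participant Selection Criteria says "123 women will be randomly assigned in a 1:1 ratio to either creatine or placebo for eight weeks", and the Design section repeats the 123.
- A footnote to Table 2A says "MA subjects with difficulty scheduling the cognitive testing appointment may be allowed to omit these measures and continue in the study".

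**The concern.** Two things look wrong. First, a single statement of more than 80% power is attached to a range of effects, and 76 participants in two arms at a level of 0.0169 looks too few for the lower end of it. Second, the effect describes a different contrast from the one tested. A gap between users and healthy subjects says how much room there is for improvement. It does not say how much more creatine improves cognition than placebo does in 8 weeks.

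The section also says the deficit is most marked in episodic memory, yet names executive and working memory as its targets.

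What is at stake is how Aim 3 is read. Cognition is one of three specific aims and carries a superiority hypothesis. A reader who trusts the stated power could take a null result as evidence against a medium-sized effect that the trial may have had well under an 80% chance of detecting.

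**Working it through.** **Inputs**

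- Level 0.0169. Sidak for three tests gives 1 − 0.95^(1/3) = 0.01695, so the plan's value reproduces (truncated).
- n = 76 at 1:1, so 38 per arm. This matches 95 × 0.8 = 76 completers.
- Effect 0.5 to 0.8 SD, from the plan.
- Two-sided test: assumption.
- Pre-post correlation r: not stated for Aim 3. I take 0.5, the HAM-D value, as the base case and vary it.

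**Method.** With two visits and complete pairs, the creatine-by-visit interaction is the between-arm difference in mean change. If Δ is that difference in raw (cross-sectional) SDs, the standardised effect is d = Δ / √(2(1 − r)), which equals Δ at r = 0.5. Adjusting follow-up for baseline (ANCOVA) gives d = Δ / √(1 − r²). Power is from the noncentral t with 74 df and noncentrality d × √(38/2) = 4.359 d. The two-sided critical value is 2.444.

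**The plan's figure, base case (r = 0.5)**

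| Δ | Noncentrality | Power |
|---|---|---|
| 0.5 | 2.18 | 40.1% |
| 0.65 | 2.83 | 65.2% |
| 0.8 | 3.49 | 84.9% |

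At 0.5 the noncentrality is below the critical value, so power is below one half. The smallest d with 80% power is 0.756. The number per arm needed for 80% is 85 at 0.5, 51 at 0.65 and 35 at 0.8. So the claim reproduces at the top of the range but not at the middle or bottom.

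**Other readings at Δ = 0.5** (r = 0.5 unless stated)

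- One-sided at 0.0169: 51%.
- Two-sided at 0.05, without Sidak: 58%.
- ANCOVA: 53%.
- 76 read as the number per arm, two-sided: 75%.
- 76 per arm and one-sided: 83%. This exceeds 80% but doubles the stated sample.
- A one-group pre-post test with n = 76: 98%. This does not compare the arms.

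**Sensitivity to r** (change score, 38 per arm, two-sided; values of r other than 0.5 are assumptions)

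| Δ | r = 0.5 | r = 0.6 | r = 0.7 | r = 0.8 |
|---|---|---|---|---|
| 0.5 | 40.1% | 50.0% | 64.4% | 83.9% |
| 0.65 | 65.2% | 76.3% | 88.5% | 97.7% |
| 0.8 | 84.9% | 92.4% | 97.9% | 99.9% |

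Reaching 80% at Δ = 0.5 requires r of about 0.78 with a change score, or 0.75 with ANCOVA.

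**If 123 are randomised.** Carrying over the 20% attrition, 123 × 0.8 = 98.4, about 49 per arm if all are tested. At r = 0.5, power is 52% at 0.5, 78% at 0.65 and 94% at 0.8, with 80% from d = 0.66. At Δ = 0.5, 80% requires r of about 0.72 (change score) or 0.66 (ANCOVA). The plan gives no rate for omitted cognitive testing, so the number with paired scores could be lower.

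**If creatine closes only part of the deficit.** As an illustration, suppose the net creatine-placebo difference is half the deficit, 0.25 to 0.40 SD. The share is my assumption. Change-score power is then:

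| Per arm | r = 0.5 | r = 0.8 |
|---|---|---|
| 38 | 9% to 25% | 24% to 62% |
| 49 | 12% to 33% | 32% to 76% |

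Under that assumption, even a correlation of 0.8 does not restore 80%.

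**The case against.** The strongest objection is that 40% is one scenario. Aim 3 states no correlation, and 0.5 is borrowed from a HAM-D calculation with ten measures. Nothing ties it to the WCST, Stroop or WMS-IV at two visits. At r = 0.8 power at 0.5 is 84%, and from r = 0.7 it is already above 80% at the midpoint of 0.65. The plan does not say that its 80% applies at 0.5 specifically, and at 0.8 it holds even in the base case. This stands to the extent that the low-end shortfall is conditional on r. It does not supply the missing correlation, without which the figure cannot be confirmed.

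The 20% attrition was stated for 95 recruits, not 123. If 123 was chosen to retain about 76 completers (76/123 = 62%), the two numbers need not conflict. The documents do not settle this, so the figures for 49 per arm are an assumption.

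The half-deficit example has no source in the plan. It is an illustration and the conclusion does not depend on it.

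The plan calls this a pilot and a feasibility study, and its overall sample size rests on HAM-D. That limits the consequence to the interpretation of Aim 3. It does not make the stated power correct.

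None of these points answers the mismatch between a user-versus-healthy deficit and a creatine-placebo interaction, which needs no assumption about r or sidedness.

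**Conclusion.** The concern holds and should be fixed. The effect size belongs to a different contrast, whatever else is assumed. Taken at face value, it supports more than 80% power only from about 0.76 SD of change with 38 per arm, or 0.66 with 49. In the base case power at 0.5 is 40% and 52% respectively, against the stated figure of more than 80%.

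These values assume a two-sided test, complete pairs in equal arms and, where effects are in raw SDs, r = 0.5. A correlation near 0.78 would rescue the low end for 38 per arm, but only if the net treatment effect equals the whole deficit. The GEE models also adjust for covariates, whose effect on precision the plan does not quantify. The finding is not that the trial lacks power at 0.8, where the base case gives 85%.

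**What to change.** Replace the sentence claiming more than 80% power with a statement of the detectable difference:

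> With [N] participants per arm expected to have both cognitive assessments, a two-sided test at the Sidak level of 0.0169 has 80% power to detect a creatine-placebo difference of [X] SD of change. The assumed pre-post correlation is [r].

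For N = 38, X = 0.76; power is 40% at 0.5 and 85% at 0.8 SD of change. For N = 49 (123 less 20%, all tested), X = 0.66; power is 52% and 94%. In SD of change these hold at any r. Give the raw-SD equivalent too, X × √(2(1 − r)): for N = 38 and r = 0.7 it is 0.76 × 0.775 = 0.59.

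Also:

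- Reconcile n = 76 with the 123 in Participant Selection Criteria and Design, and state the attrition that applies to 123.
- State the allowance for participants who omit cognitive testing under the Table 2A footnote.
- Remove the user-versus-healthy deficit as the treatment effect, or state what share of it creatine is assumed to close relative to placebo, and why.

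The cost is rewording, with no extra participants and no change to visits or test. The stated power becomes less favourable, and the authors must commit to a correlation and an expected number with paired scores.
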